#### Interim Safety Review

Given the need for rapid review and dissemination of study data for public health reasons, AEs and SAEs may be reviewed as necessary outside of DSMB reviews. The DSMB will not need to meet unless halting rules are met, or as requested by the sponsor or PI, and materials will be provided electronically. Documentation of review and any concerns noted will be solicited electronically.

Safety reviews for sentinel halting rules by the protocol team and for dose escalation criteria by the SSC are described in Sections 8.5.1 and 8.1.6 of the protocol. Additional safety reviews may be conducted as necessary.

#### Safety Reviews by the DSMB

Given the frequency and urgency to review data, the DSMB will not need to meet to assess sentinel halting rules or dose escalation criteria unless halting rules are met or as requested by the SSC.

If any of the halting rules listed in Sections 8.5.1 and 8.5.2 of the protocol are met, cumulative safety data from all enrolled participants will be summarized for DSMB review.

If no halting rules are met, or in addition to unscheduled DSMB reviews, the DSMB will review cumulative AE data as follows:

- After all participants in Groups 1, 3A, 3B, and 4 have completed Day 8 post first study vaccination visit.
- After all participants in Groups 1, 3A, 3B and 4 have completed Day 8 post second study vaccination visit.

- After all participants in Groups 5-7, 9, 10, 11, and 13-15 have completed Day 8 post study vaccination visit.
- After all participants in Groups 8 and 12 have completed Day 8 post first study vaccination visit.

The DSMB reviews listed above do not have to occur in a sequential manner and may be combined if milestones are reached on dates that are close together.

In addition, the DSMB will meet to review available safety data after all participants in all groups enrolled in Stages 1 and 2 have completed the visit that occurs 28 days after their last study vaccination.

Ad hoc safety reports may also be prepared for DSMB review as deemed necessary and appropriate by DMID.

Materials for all DSMB reviews will be provided electronically. Documentation of review and any concerns noted will be solicited electronically.

### **Interim Immunogenicity Review**

Interim data review of immunogenicity may be performed to inform public health decisions.

Statistical analyses of secondary immunogenicity endpoints, by vaccine schedule group, may be performed when participants have completed key immunogenicity visits. Immunogenicity reviews may be shared with the DSMB, as determined by DMID. Immunogenicity reports may be combined with safety reports if projected milestones for reports will occur close enough to each other where, in the opinion of the protocol team, producing one report, as opposed to two separate reports, is more informative regarding the safety of participants and more beneficial to the overall needs of the protocol team.

Data may be disseminated to public health officials and partners as needed. In addition, participants will be informed regarding interim aggregate antibody results after the 4-week timepoint after the last study vaccination.

## **6.3. Analysis Populations**

### **6.3.1. Modified Intention-to-Treat (mITT) Population**

The modified Intention-to-Treat (mITT) population includes all participants who received at least one dose of the study vaccination and contributed both pre- and at least one post-dose venous blood samples for immunogenicity testing for which valid results were reported. All analyses of the immunogenicity data will be completed for the mITT population

### **6.3.2. Per Protocol Population**

In the final analysis, protocol deviations will be reviewed to determine which protocol deviations may affect the analysis. The per protocol (PP) population will then be specified and this includes all participant-visits in the mITT population with the following exclusions:

1. Data from all available visits for participants found to be ineligible at baseline.
2. Data from all visits after protocol deviations that are considered to affect the analysis.
3. Data from all visits after the receipt of an out-of-study COVID-19 vaccine.
4. Data from all visits after a post-baseline COVID-19 infection.
5. Data from any visit that occurs substantially out of window.

COVID-19 infection will be determined by self-report and the ELISA SARS-CoV-2 Nucleoprotein IgG (N-Antibody) assay, which tests for antibodies to the N-protein as an indicator of previous COVID-19 infection. This assay will return a result of negative or positive for previous COVID-19 infection.

All analyses of the immunogenicity data will be completed for the per protocol population.

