### 7.2. Protocol Deviations

A summary of participant-specific protocol deviations will be presented by the reason for the deviation, the deviation category, and the vaccination arm for all deviations ([Table 9](#), [Table 10](#), [Table 11](#), [Table 12](#), and [Table 13](#)) and major deviations only ([Table 14](#), [Table 15](#), [Table 16](#), [Table 17](#), and [Table 18](#)). Ineligibility or product administration deviations will be considered major deviations and reviewed for possible participant exclusion from the per protocol population. Other protocol deviations may be considered major deviations, as determined by DMID. All participant specific protocol deviations and non-participant specific protocol deviations will be included in [Listing 3](#) and [Listing 4](#).

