## 10.2 Protocol Deviations

**Table 9: Distribution of Protocol Deviations by Category, Type, and Vaccination Arm - COVID-19 Vaccination Naïve, 18-60 years of age, Groups 1 and 3A**

Category	Deviation Type	Group 1: 5 x 10  vp ChAd-S/ 30 µg SAM-S (N=X)		Group 3A: 30 µg SAM-S/ 30 µg SAM-S (N=X)		All Participants (N=X)	
		# of Ppt.	# of Dev.	# of Ppt.	# of Dev.	# of Ppt.	# of Dev.
Eligibility/enrollment	Any type	x	x	x	x	x	x
	Did not meet inclusion criterion						
	Met exclusion criterion						
	ICF not signed prior to study procedures						
	Other						
Vaccination schedule	Any type						
	Out of window visit						
	Missed visit/visit not conducted						
	Missed Vaccination						
	Delayed Vaccination						
	Other						
Follow-up visit schedule	Any type						
	Out of window visit						
	Missed visit/visit not conducted						
	Other						
Protocol procedure/assessment	Any type						
	Incorrect version of ICF signed						
	Blood not collected						
	Urine not collected						
	Other specimen not collected						
	Too few aliquots obtained						

Category	Deviation Type	Group 1: $5 \times 10^{10}$ vp ChAd-S/ 30 µg SAM-S (N=X)		Group 3A: 30 µg SAM-S/ 30 µg SAM-S (N=X)		All Participants (N=X)	
		# of Ppt.	# of Dev.	# of Ppt.	# of Dev.	# of Ppt.	# of Dev.
	Specimen result not obtained						
	Required procedure not conducted						
	Required procedure done incorrectly						
	Specimen temperature excursion						
	Other						
Vaccine administration	Any type						
	Required procedure done incorrectly						
	Study product temperature excursion						
	Other						

Tables with similar format:

**Table 10: Distribution of Protocol Deviations by Category, Type, and Vaccination Arm - COVID-19 Vaccination Naïve, 18-60 years of age, Groups 3B and 4**

**Table 11: Distribution of Protocol Deviations by Category, Type, and Vaccination Arm – COVID-19 mRNA Vaccinated, 18-60 years of age, SAM-S-TCE Boosts**

**Table 12: Distribution of Protocol Deviations by Category, Type, and Vaccination Arm – COVID-19 mRNA Vaccinated, >60 years of age, SAM-S-TCE Boosts**

**Table 13: Distribution of Protocol Deviations by Category, Type, and Vaccination Arm – COVID-19 mRNA Vaccinated, >60 years of age, ChAd-S-TCE Boosts**

**Table 14: Distribution of Major Protocol Deviations by Category, Type, and Vaccination Arm – COVID-19 Vaccination Naïve, 18-60 years of age, Groups 1 and 3A**

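### Per-protocol rule 2 removes only the visits after a relevant deviation, so one confined to a single visit keeps its suspect result and loses the sound later ones

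*SAP*

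**What the plan says.** Section 6.3.2 of the SAP defines the PP population by participant-visit: "this includes all participant-visits in the mITT population with the following exclusions". Before that, "protocol deviations will be reviewed to determine which protocol deviations may affect the analysis". For the deviations that pass this review, rule 2 excludes "Data from all visits after protocol deviations that are considered to affect the analysis". The only exclusion that acts on a single visit is rule 5: "Data from any visit that occurs substantially out of window".

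Section 7.2 says which deviations are sent to PP review: "Ineligibility or product administration deviations will be considered major deviations and reviewed for possible participant exclusion from the per protocol population". It then adds: "Other protocol deviations may be considered major deviations, as determined by DMID".

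Table 9 (Appendix 1, section 10.2) lists the deviation types to be tabulated. Among them are "Specimen temperature excursion" and "Required procedure done incorrectly".

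**The concern.** Rule 2 looks forward in time whatever the type of deviation. After a wrong or mistimed dose this is right: blood drawn before the dose at that visit is still valid, and everything later is affected. When one specimen or procedure is compromised, it works the wrong way round. The doubtful result belongs to the visit of the deviation, which the rule does not name, and the later samples that it removes have nothing wrong with them.

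At stake are the PP geometric means, fold rises and T cell summaries. A doubtful result could stay in the summary for its own visit, and the durability visits could lose a sound participant. The groups are small (3 to 12 participants in Table 2), so one person is 8% to 33% of a group (1/12 to 1/3).

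**Working it through.** **Applying the rule to the schedule.** For the enrolled Stage 2 groups, section 4.5 gives antibody and ELISpot samples at Day 1 and at five post-dose visits: Days 15, 29, 85, 181 and 366. Take a specimen deviation confined to one post-dose visit and judged to affect the analysis.

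| Deviation at | Rule 2 drops | Affected visit | A visit-only rule would drop |
|---|---|---|---|
| Day 15 | Days 29, 85, 181, 366 | kept | Day 15 |
| Day 29 | Days 85, 181, 366 | kept | Day 29 |
| Day 85 | Days 181, 366 | kept | Day 85 |
| Day 181 | Day 366 | kept | Day 181 |
| Day 366 | nothing | kept | Day 366 |

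For ICS, Day 15 is the only post-dose time point in these groups, so a Day 15 deviation removes no ICS result at all.

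**Whether another provision repairs this.** Rule 5 covers only out-of-window visits. The valid-result wording in the mITT definition (section 6.3.1) is a condition for a participant to enter (a pre-dose and at least one post-dose sample), not a filter on each visit. The deviation review decides which deviations count, and rule 2 then fixes which visits go. The note to Listing 5 asks that exclusion reasons agree with the SAP text, so a sensible visit-only exclusion would depart from the plan.

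**Size of a needless loss.** The interval is GMT × exp(± t(0.975, n−1) × SD / √n). As a check, with GMT 100, SD 1.0 and n=7 it gives (39.7, 252.1), as printed in Table 5.

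The log-scale half-width is proportional to t(0.975, n−1)/√n:

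- n=7 to 6: 2.447/√7 = 0.925 and 2.571/√6 = 1.049, which is 13.5% wider.
- n=8 to 7: 2.365/√8 = 0.836 and 0.925, which is 10.6% wider.
- n=10 to 9: 2.262/√10 = 0.715 and 2.306/√9 = 0.769, which is 7.5% wider.

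At SD 1.0 and GMT 100, going from n=7 to n=6 moves the interval from (39.7, 252.1) to (35.0, 285.6). The upper/lower ratio rises from exp(2 × 0.925) = 6.4 to exp(2 × 1.049) = 8.2.

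**Size of a retained bad result.** The SAP gives no figure for this, so both the size and the direction of the error are assumed. One titre falsely low by a factor f multiplies the visit GMT by f^(−1/n). At n=7, f=2 gives 0.906 and f=5 gives 0.795, a fall of 9% to 21%.

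**The case against.** The strongest reply is that rule 2 is filtered. It covers only deviations that the review considers relevant, and the types section 7.2 names for PP review are ineligibility, which has its own rule 1, and product administration, for which a forward-looking exclusion is correct. Table 9 is a reporting shell, not a list of PP triggers.

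This limits the reach of the point but does not remove it. Rule 2 is not restricted to dosing, and section 7.2 lets DMID class other deviations as major. If a specimen or procedure deviation does pass the filter, no other visit rule applies to it.

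A second reply is that a compromised specimen may never yield a result. The laboratory may void it, and Table 9 has a type for results not obtained. That could well happen, but the PP rules do not require it, and voiding the specimen would not bring back the later visits.

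A third is that the Listing 5 shell already gives a day-level exclusion as an example. It does, so the reporting format can carry a visit-only exclusion. It does not supply a rule for one.

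The last reply stands in full: the consequence is small. PP is one of two populations for descriptive secondary summaries. The mITT tables keep the later results, individual responses are listed, no hypothesis is tested, and the primary safety endpoints use another population.

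**Conclusion.** The point holds in a conditional form, at low severity. For a deviation confined to one visit or specimen and judged to affect the analysis, rule 2 as written keeps any reported result from that visit and removes unaffected later ones. Each needless loss costs about 7.5% to 13.5% in log-scale CI width at group sizes of 10 down to 7. The 9% to 21% shift in GMT from a retained bad titre is an illustration resting on an assumed 2- to 5-fold error.

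Two stronger readings are tempting, and the SAP supports neither. One is that any deviation costs a participant all later visits: the rule reaches only those judged relevant. The other is that the PP tables will contain results known to be unreliable: the SAP does not say that such results will be reported, and it gives no expected number of such deviations.

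**What to change.** Split rule 2 in section 6.3.2:

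- (a) For a deviation with a lasting effect, such as a product administration error, exclude results from samples taken after the deviation.
- (b) For a deviation confined to a visit or specimen, exclude only the affected result or results at that visit, the visit of the deviation included, and keep later visits.

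If the affected sample is the baseline, say also that fold rises depending on it are dropped.

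The cost is about two sentences in section 6.3.2 and one flag (lasting or visit-only) on each reviewed deviation. Setting this before the final deviation review avoids choosing the visits to exclude with results in hand.

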### **6.3.3. Safety Population**

The safety population will consist of all participants who received at least one dose of a study vaccine. All analyses of safety data will be completed for the safety population.

## **6.4. Covariates and Subgroups**

The protocol does not define any formal subgroup analyses, and the study is not adequately powered to perform subgroup analyses.

## **6.5. Missing Data**

There are no imputations planned for missing data. For neutralization assays, any percent neutralization below zero will be imputed as zero for analyses. For assays with a lower limit of detection (LLOD) or a lower limit of quantification (LLOQ), any results below the LLOD/LLOQ will be imputed as one-half the LLOD/LLOQ. For the ICS assay, results below 0.001 will be imputed as 0.001.

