### **Sample size calculations for SARS-CoV-2-specific antibody binding and neutralization titer in serum**

A secondary endpoint of this study is to evaluate the magnitude of SARS-CoV-2-specific antibody binding and neutralization titers in serum samples. This endpoint is descriptive in nature and will be accomplished by estimating the geometric mean titer (GMT) at each timepoint when samples are collected.

The precision with which a true GMT can be estimated from observed data depends on the standard deviation (SD) of the measurements, in the logarithmic scale, and the sample size. [Table 5](#) displays two-sided 95% confidence intervals for the GMT for several values of the observed antibody titer.

**Table 5: Two-sided 95% confidence intervals based on observing a particular average loge antibody titer in participants' groups, taking 0% or 20% attrition into consideration (n = 12, 10, 8, 7)**

Observed average log e antibody titer	SD of log e antibody titer	95% confidence interval			
		n=12	n = 10	n = 8	n=7
log e (5)	0.5	(3.6, 6.9)	(3.5, 7.2)	(3.3, 7.6)	(3.1,7.9)
log e (20)		(14.6, 27.5)	(14, 28.6)	(13.2, 30.4)	(12.6,31.8)
log e (50)		(36.4, 68.7)	(35, 71.5)	(32.9, 75.9)	(31.5,79.4)
log e (100)		(72.8, 137.4)	(69.9, 143)	(65.8, 151.9)	(63,158.8)
log e (250)		(182, 343.5)	(174.8, 357.5)	(164.6, 379.7)	(157.4,397)
log e (500)		(363.9, 687)	(349.6, 715)	(329.2, 759.5)	(314.9,794)
log e (1000)		(727.8, 1373.9)	(699.3, 1430)	(658.4, 1518.9)	(629.8,1587.9)
log e (5)	1.0	(2.6, 9.4)	(2.4, 10.2)	(2.2, 11.5)	(2,12.6)
log e (20)		(10.6, 37.8)	(9.8, 40.9)	(8.7, 46.1)	(7.9,50.4)
log e (50)		(26.5, 94.4)	(24.5, 102.2)	(21.7, 115.4)	(19.8,126.1)
log e (100)		(53, 188.8)	(48.9, 204.5)	(43.3, 230.7)	(39.7,252.1)
log e (250)		(132.4, 471.9)	(122.3, 511.2)	(108.4, 576.8)	(99.1,630.4)
log e (500)		(264.9, 943.9)	(244.5, 1022.5)	(216.7, 1153.6)	(198.3,1260.7)
log e (1000)		(529.7, 1887.7)	(489, 2044.9)	(433.4, 2307.2)	(396.6,2521.5)

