T cell responses to ChAd-S or ChAd-S-TCE, and SAM-S or SAM-S-TCE will be assessed by IFN- $\gamma$  ELISpot and ICS assays. The results of the IFN- $\gamma$  ELISpot assay will be summarized at all available time points in tables (starting with [Table 192](#) and ending with [Table 201](#)) by the mean with a 95% CI, median, min, and max and in figures showing the distribution of responses over time (starting with [Figure 283](#) and ending with [Figure 392](#)). The results of the ICS assay will be summarized at all available time points in tables (starting with [Table 202](#) and ending with [Table 211](#)) by the mean with a 95% CI, median, min, max, and response rate with a 95% CI. The distribution of results over time and the response rate will be presented in figures, starting with [Figure 393](#) and ending with [Figure 542](#). For the ICS assay, results below 0.001 will be imputed as 0.001.

CIs for means, GMs, GMFRs, and GMRs will be calculated using the Student's t-distribution and CIs for seropositive rates and response rates will be calculated using the Clopper-Pearson binomial method.

If additional immunological assays are determined to be necessary, then the results will be summarized in a similar manner to that of the assays described above.

Individual immunogenicity responses are shown in [Listing 8](#).

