**Table 70:** **Summary of ELISA IgG Antibody Against SARS-CoV-2 RBD by Time Point and Vaccination Arm – COVID-19 mRNA Vaccinated, >60 years of age, ChAd-S-TCE Boosts, mITT Population**

**Table 71:** **Summary of ELISA IgG Antibody Against SARS-CoV-2 RBD by Time Point and Vaccination Arm – COVID-19 mRNA Vaccinated, >60 years of age, ChAd-S-TCE Boosts, Per Protocol Population**

**Table 72: Summary of Pseudovirus Neutralizing Antibody ID50 Against SARS-CoV-2 D614G by Time Point and Vaccination Arm - COVID-19 Vaccination Naïve, 18-60 years of age, Groups 1 and 3A, mITT Population**

Time Point	Statistic	Group 1: $5 \times 10^{10}$ vp ChAd-S/30 µg SAM-S (N=X)	Group 3A: 30 µg SAM-S/30 µg SAM-S (N=X)	All Participants (N=X)
Day 1 (Pre-Vaccination 1)	n			
	GMT (95% CI)			
	Seropositive (95% CI)			
Day 29 Post Vaccination 1	n			
	GMT (95% CI)			
	GMR D614G (95% CI)			
	GMFR (95% CI)			
	Seropositive (95% CI)			
Day 57 Post Vaccination 1 (29 Days Post Vaccination 2)	n			
	GMT (95% CI)			
	GMR D614G (95% CI)			
	GMFR (95% CI)			
	Seropositive (95% CI)			
Day 209 Post Vaccination 1 (181 Days Post Vaccination 2)	n			
	GMT (95% CI)			
	GMR D614G (95% CI)			
	GMFR (95% CI)			
	Seropositive (95% CI)			
Day 391 Post Vaccination 1 (366 Days Post Vaccination 2)	n			
	GMT (95% CI)			
	GMR D614G (95% CI)			
	GMFR (95% CI)			
	Seropositive (95% CI)			

Notes: N = Number of participants enrolled

n = Number of participants in the mITT population with available results

GMT = Geometric Mean Titer, GMFR = Geometric Mean Fold Rise, GMRD614G = Geometric Mean Ratio to D614G**Implementation Notes:**Remove the row and footnote for GMRD614G from the tables for D614G.

For the Groups 1 and 3A tables, the time points should be Day 1 (Pre-Vaccination 1), Day 29 Post Vaccination 1, Day 57 Post Vaccination 1 (29 Days Post Vaccination 2), Day 209 Post Vaccination 1 (181 Days Post Vaccination 2), Day 391 Post Vaccination 1 (366 Days Post Vaccination 2).

For the Groups 3B and 4 tables, the time points should be Day 1 (Pre-Vaccination 1), Day 29 Post Vaccination 1, Day 57 Post Vaccination 1, Day 85 Post Vaccination 1, Day 99 Post Vaccination 1 (15 Days Post Vaccination 2), Day 113 Post Vaccination 1 (29 Days Post Vaccination 2), Day 169 Post Vaccination 1 (85 Days Post Vaccination 2), Day 265 Post Vaccination 1 (181 Days Post Vaccination 2), Day 450 Post Vaccination 1 (366 Days Post Vaccination 2).

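### Student t intervals are computed on half-limit values as if measured: a cell with every result below the assay limit gets a zero-width 95% CI, and cells with nearly all results below under-cover

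*SAP*

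**What the plan says.** Section 6.5 gives one rule for assays with a detection or quantification limit: "any results below the LLOD/LLOQ will be imputed as one-half the LLOD/LLOQ". Section 8.2 states that "CIs for means, GMs, GMFRs, and GMRs will be calculated using the Student's t-distribution", and asks for these summaries for each group at each time point. The Appendix 1 shells apply this from Day 1 onward: Tables 52-71 (ELISA) and Tables 72-191 (pseudovirus and FRNT) all have a GMT with 95% CI, including the pre-vaccination row in the naive groups. Figures 3-142 plot the same means and intervals.

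Section 5 says the precision of a GMT "depends on the standard deviation (SD) of the measurements, in the logarithmic scale, and the sample size". Table 5 then shows intervals for ln SD 0.5 and 1.0 and makes no allowance for results below a limit.

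For the neutralization assays, Section 8.2 adds a seropositive rate (the share above the LLOD) with a Clopper-Pearson CI. Neither the ELISA text nor the ELISA shell has that row. The SAP gives no limit values, no expected share below the limit, no censored-data method and no sensitivity analysis.

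**The concern.** A result below the limit is known only to lie below it. Replacing it with a constant and computing a t interval treats that constant as a measurement. The spread of the substituted values then enters the SD as real information about variability.

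The effect is worst where the assay says least. A cell in which nothing was detected prints the tightest interval in the table. A cell in which nearly nothing was detected prints an interval centred largely on the chosen constant. Section 5 describes the antibody-magnitude endpoint as descriptive and met by estimating GMTs, so with no tests planned the interval is the only statement of uncertainty about the titre.

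**Working it through.** **Inputs.** ln SD 0.5 and 1.0, and n = 7, 8, 10, 12, from Table 5. n = 4, 3, 7, 3 for Groups 1, 3A, 3B and 4, from Table 2. The true share f below the limit is not in the SAP, so it is varied.

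**1. Reproducing Table 5.** Interval = GMT × exp(± t(0.975, n−1) × SD/√n). For GMT 100 and SD 1.0:
- n = 12: t = 2.201, giving (53.0, 188.8)
- n = 10: t = 2.262, giving (48.9, 204.5)
- n = 8: t = 2.365, giving (43.3, 230.7)
- n = 7: t = 2.447, giving (39.7, 252.1)

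These match the printed values. Table 5 therefore describes titres that are all measured.

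**2. All results below the limit L.** Every log value is ln(L/2), so SD = 0 and the half-width is t × 0/√n = 0. The cell prints L/2 (L/2, L/2). The probability is f^n:

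| f | n=3 | n=4 | n=7 | n=10 | n=12 |
|---|---|---|---|---|---|
| 0.5 | 12.5% | 6% | 0.8% | 0.1% | <0.1% |
| 0.75 | 42% | 32% | 13% | 6% | 3% |
| 0.8 | 51% | 41% | 21% | 11% | 7% |
| 0.9 | 73% | 66% | 48% | 35% | 28% |

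**3. Some results above the limit.** Simulation with 200,000 samples per setting: normal ln titres, values below L set to L/2, t interval on the log scale. Coverage is of the true, uncensored GMT, with zero-width cells counted as misses:

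| f | SD 1.0, n=7-12 | SD 0.5, n=7-12 |
|---|---|---|
| 0.5 | 94% | 86-90% |
| 0.6 | 93-94% | 83-87% |
| 0.7 | 89-92% | 81-82% |
| 0.75 | 80-82% | 80-84% |
| 0.8 | 63% (n=7) falling to 10% (n=12) | 79-83% |
| 0.9 | about 0% | 52-71% |
| 0.95 | 0% | 2-29% |

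With almost nothing below the limit, coverage is 95%, as it should be. At n = 3 and SD 1.0 it is 85% at f = 0.5 and 57% at f = 0.75. At SD 1.0 and n = 7-12 the median reported GMT is about 1.45 times the truth at f = 0.8 and about 2 times at f = 0.9.

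**4. Why coverage collapses where it does.** No value entering the mean can be less than L/2. The true GMT falls below L/2 once SD × z(f) > ln 2 = 0.693. At SD 1.0 that is z > 0.693, or f above about 0.76. At SD 0.5 it is z > 1.386, or f above about 0.92. Beyond that point the estimate always exceeds the truth, and a larger n only tightens the interval around the wrong value.

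**5. What the companion row shows.** For 0 of n seropositive, the Clopper-Pearson upper limit is 1 − 0.025^(1/n): 71% (n=3), 60% (n=4), 41% (n=7), 31% (n=10), 26% (n=12). A neutralization table can therefore show 0% with an upper limit of 71% beside a GMT interval of zero width. An ELISA table shows only the zero width.

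**6. A censored alternative.** A left-censored normal likelihood with profile CI (600 samples per setting; n = 10 and 12; f = 0.5, 0.7, 0.8; both SDs) covered 94-99% when at least 2 results were above the limit. That condition failed in about 0-1%, 9-16% and 27-39% of samples at the three values of f.

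**The case against.** The strongest reply is that little hangs on these intervals. Section 6.8 plans no hypothesis tests. In 120 of the 140 GMT tables the seropositive rate with exact CI appears in the same cell. The distribution figures (143-282) and Listing 8 show the individual values. This stands, and it keeps the matter moderate. It does not reach the 20 ELISA tables, and it does not make a zero-width 95% interval a correct one.

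Several stronger readings are tempting, and the documents do not support them:
- **That zero width follows when most results are below.** It needs all of them below. At f = 0.5 and n = 7 that happens in 0.8% of cells, and at 50-70% below with n = 7-12 coverage is still 81-94%.
- **That Omicron-variant ID80 cells will mostly fall below the limit.** The SAP gives neither limits nor expected shares. Only Day 1 in naive participants can be inferred from the design.
- **That all 140 tables and 140 figures are affected.** They carry the method, but the share of affected cells is unknown, and 84 of the 140 tables concern mRNA-vaccinated cohorts.
- **That the coverage figures describe Day 1 in naive participants.** In antibody-negative people a true GMT below the limit has little meaning. The fault there is false precision, not a missed target.

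**Conclusion.** The point holds, at moderate weight. The zero-width interval follows directly from Sections 6.5 and 8.2 whenever a whole cell is below the limit, and the naive groups of 3, 4 and 7 at Day 1 make that plausible. For partly censored cells at n = 7-12, under-coverage is modest to moderate at 50-75% below (about 80-95%). It is severe from about 80% below at ln SD 1.0, or 90% at ln SD 0.5. It sets in earlier in groups of 3 or 4.

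The coverage figures assume a lognormal distribution that continues below the limit, the two planning SDs of Table 5, and an assumed share below. GMFR and GMR are built from the same substituted values and so are exposed to the same problem, but they were not simulated.

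**What to change.** Amend Sections 6.5 and 8.2, the GMT shells and the figure notes:

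1. Where all results in a group-by-visit cell are below the limit, print <LLOD (or <LLOQ) with no CI, and plot the cell that way in Figures 3-142.
2. Print the number of results below the limit in every GMT cell, including ELISA Tables 52-71.
3. Where some but not all are below, keep the half-limit GMT as planned. If at least 2 results are above the limit, add a left-censored lognormal estimate with profile-likelihood CI as a sensitivity analysis. If not, flag the t interval as unreliable.

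Do not use a blanket rule that replaces the GMT by <LLOD once half the results are below. At ln SD 1.0 and n = 7-12 it would discard intervals with about 94% coverage, and it can state something false. With 40% truly below at SD 1.0, the true GMT is exp(0.253) = 1.29 times the limit, yet 5 or more of 10 results fall below in 37% of samples.

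The cost is SAP wording and a little more programming. A few cells lose a printed interval.
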